8 STUDY ASSESSMENTS AND PROCEDURES

8.1 EFFICACY ASSESSMENTS

Efficacy will be assessed with patient-reported outcome measures, including the Numeric Pain Rating Scale (NPRS), Patient Rated Wrist/Hand Evaluation (PRWHE), and Single Assessment Numeric Evaluation (SANE), on a weekly basis.

8.2 SAFETY AND OTHER ASSESSMENTS

Participants will additionally report any adverse events, oral analgesic use, or thumb CMC splint use on a weekly basis.

8.3 ADVERSE EVENTS AND SERIOUS ADVERSE EVENTS

8.3.1 DEFINITION OF ADVERSE EVENTS (AE)

Adverse event means any untoward medical occurrence associated with the use of an intervention in humans, whether or not considered intervention-related (21 CFR 312.32 (a)).

8.3.2 DEFINITION OF SERIOUS ADVERSE EVENTS (SAE)

An adverse event (AE) or suspected adverse reaction is considered "serious" if, in the view of either the investigator or sponsor, it results in any of the following outcomes: death, a life-threatening adverse event, inpatient hospitalization or prolongation of existing hospitalization, a persistent or significant incapacity or substantial disruption of the ability to conduct normal life functions, or a congenital anomaly/birth defect. Important medical events that may not result in death, be life-threatening, or require hospitalization may be considered serious when, based upon appropriate medical judgment, they may jeopardize the participant and may require medical or surgical intervention to prevent one of the outcomes listed in this definition. Examples of such medical events include allergic bronchospasm requiring intensive treatment in an emergency room or at home, blood dyscrasias or convulsions that do not result in inpatient hospitalization, or the development of drug dependency or drug abuse.

8.3.3 CLASSIFICATION OF AN ADVERSE EVENT

8.3.3.1 SEVERITY OF EVENT

For adverse events (AEs) not included in the protocol defined grading system, the following guidelines will be used to describe severity.

- Mild Events require minimal or no treatment and do not interfere with the participant's daily activities.
- Moderate Events result in a low level of inconvenience or concern with the therapeutic measures. Moderate events may cause some interference with functioning.
- **Severe** Events interrupt a participant's usual daily activity and may require systemic drug therapy or other treatment. Severe events are usually potentially life-threatening or incapacitating. Of note, the term "severe" does not necessarily equate to "serious".

8.3.3.2 RELATIONSHIP TO STUDY INTERVENTION

All adverse events (AEs) must have their relationship to study intervention assessed by the clinician who examines and evaluates the participant based on temporal relationship and his/her clinical judgment. The degree of certainty about causality will be graded using the categories below. In a clinical trial, the study product must always be suspect.

- **Related** The AE is known to occur with the study intervention, there is a reasonable possibility that the study intervention caused the AE, or there is a temporal relationship between the study intervention and event. Reasonable possibility means that there is evidence to suggest a causal relationship between the study intervention and the AE.
- **Not Related** There is not a reasonable possibility that the administration of the study intervention caused the event, there is no temporal relationship between the study intervention and event onset, or an alternate etiology has been established.

8.3.3.3 EXPECTEDNESS

The Principal Investigator will be responsible for determining whether an adverse event (AE) is expected or unexpected. An AE will be considered unexpected if the nature, severity, or frequency of the event is not consistent with the risk information previously described for the study intervention.

8.3.4 TIME PERIOD AND FREQUENCY FOR EVENT ASSESSMENT AND FOLLOW-UP

The occurrence of an adverse event (AE) or serious adverse event (SAE) may come to the attention of study personnel during study visits and interviews of a study participant presenting for medical care, or upon review by a study monitor.

All AEs including local and systemic reactions not meeting the criteria for SAEs will be captured on the weekly questionnaires. All AEs occurring while on study must be documented appropriately regardless of relationship. All AEs will be followed to adequate resolution.

Any medical condition that is present at the time that the participant is screened will be considered as baseline and not reported as an AE. However, if the study participant's condition deteriorates at any time during the study, it will be recorded as an AE.

Changes in the severity of an AE will be documented to allow an assessment of the duration of the event at each level of severity to be performed. AEs characterized as intermittent require documentation of onset and duration of each episode.

The research coordinator will record all reportable events with start dates occurring any time after informed consent. Events will be followed for outcome information until resolution or stabilization.

8.3.5 ADVERSE EVENT REPORTING

Adverse events will reported to the Principal Investigator who is responsible for data and safety monitoring.

8.3.6 SERIOUS ADVERSE EVENT REPORTING

The study clinician will immediately report to the sponsor any serious adverse event, whether or not considered study intervention related, including those listed in the protocol or investigator brochure and must include an assessment of whether there is a reasonable possibility that the study intervention

caused the event. Study endpoints that are serious adverse events (e.g., all-cause mortality) must be reported in accordance with the protocol unless there is evidence suggesting a causal relationship between the study intervention and the event (e.g., death from anaphylaxis). In that case, the investigator must immediately report the event to the sponsor.

All serious adverse events (SAEs) will be followed until satisfactory resolution or until the site investigator deems the event to be chronic or the participant is stable. Other supporting documentation of the event may be requested by the Data Coordinating Center (DCC)/study sponsor and should be provided as soon as possible.

The study sponsor will be responsible for notifying the Food and Drug Administration (FDA) of any unexpected fatal or life-threatening suspected adverse reaction as soon as possible, but in no case later than 7 calendar days after the sponsor's initial receipt of the information. In addition, the sponsor must notify FDA and all participating investigators in an Investigational New Drug (IND) safety report of potential serious risks, from clinical trials or any other source, as soon as possible, but in no case later than 15 calendar days after the sponsor determines that the information qualifies for reporting.]

8.3.7 REPORTING EVENTS TO PARTICIPANTS

Not applicable.

8.3.8 EVENTS OF SPECIAL INTEREST

Not applicable.

8.3.9 REPORTING OF PREGNANCY

Not applicable.

8.4 UNANTICIPATED PROBLEMS

8.4.1 DEFINITION OF UNANTICIPATED PROBLEMS (UP)

The Office for Human Research Protections (OHRP) considers unanticipated problems involving risks to participants or others to include, in general, any incident, experience, or outcome that meets all of the following criteria:

- Unexpected in terms of nature, severity, or frequency given (a) the research procedures that are
 described in the protocol-related documents, such as the Institutional Review Board (IRB)approved research protocol and informed consent document; and (b) the characteristics of the
 participant population being studied;
- Related or possibly related to participation in the research ("possibly related" means there is a
 reasonable possibility that the incident, experience, or outcome may have been caused by the
 procedures involved in the research); and
- Suggests that the research places participants or others at a greater risk of harm (including physical, psychological, economic, or social harm) than was previously known or recognized.

[This definition could include an unanticipated adverse device effect, any serious adverse effect on health or safety or any life-threatening problem or death caused by, or associated with, a device, if that

effect, problem, or death was not previously identified in nature, severity, or degree of incidence in the investigational plan or application (including a supplementary plan or application), or any other unanticipated serious problem associated with a device that relates to the rights, safety, or welfare of subjects (21 CFR 812.3(s)).

8.4.2 UNANTICIPATED PROBLEM REPORTING

The investigator will report unanticipated problems (UPs) to the reviewing Institutional Review Board (IRB) and to the Data Coordinating Center (DCC)/principal investigator (PI). The UP report will include the following information:

- Protocol identifying information: protocol title and number, PI's name, and the IRB project number;
- A detailed description of the event, incident, experience, or outcome;
- An explanation of the basis for determining that the event, incident, experience, or outcome represents an UP;
- A description of any changes to the protocol or other corrective actions that have been taken or are proposed in response to the UP.

To satisfy the requirement for prompt reporting, UPs will be reported using the following timeline:

- UPs that are serious adverse events (SAEs) will be reported to the IRB and to the DCC/study sponsor within <insert timeline in accordance with policy> of the investigator becoming aware of the event.
- Any other UP will be reported to the IRB and to the DCC/study sponsor within <insert timeline in accordance with policy> of the investigator becoming aware of the problem.
- All UPs should be reported to appropriate institutional officials (as required by an institution's
 written reporting procedures), the supporting agency head (or designee), and the Office for
 Human Research Protections (OHRP) within <insert timeline in accordance with policy> of the
 IRB's receipt of the report of the problem from the investigator.]

An investigator shall submit to the sponsor and to the reviewing Institutional Review Board (IRB) a report of any unanticipated adverse device effect occurring during an investigation as soon as possible, but in no event later than 10 working days after the investigator first learns of the effect (21 CFR 812.150(a)(1)), A sponsor who conducts an evaluation of an unanticipated adverse device effect under 812.46(b) shall report the results of such evaluation to the Food and Drug Administration (FDA) and to all reviewing IRB's and participating investigators within 10 working days after the sponsor first receives notice of the effect. Thereafter the sponsor shall submit such additional reports concerning the effect as FDA requests (21 CFR 812.150(b)(1)).

8.4.3 REPORTING UNANTICIPATED PROBLEMS TO PARTICIPANTS Not applicable.

STATISTICAL CONSIDERATIONS

9.1 STATISTICAL HYPOTHESES

• Primary Efficacy Endpoint(s):

Numeric Pain Rating Scale (NPRS) at 4 weeks

• Secondary Efficacy Endpoint(s):

Numeric Pain Rating Scale (NPRS) at 6 weeks Patient Rated Wrist/Hand Evaluation (PRWHE) at 4 and 6 weeks Single Assessment Numeric Evaluation (SANE) at 4 and 6 weeks

9.2 SAMPLE SIZE DETERMINATION

A sample size of 54 participants (27 in each group, allowing for 10% withdrawals) was calculated to detect an estimated effect size of 1 in NPRS with a power of 0.80 and alpha of 0.05.

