1 PROTOCOL SUMMARY

1.1 SYNOPSIS

Title: Pulsed Electromagnetic Field (PEMF) Therapy in Thumb CMC Arthritis

Study Description: Thumb carpometacarpal (CMC) osteoarthritis (OA) is a common source of

hand pain with limited non-operative treatment options. Pulsed

electromagnetic field (PEMF) therapy has been recently shown in studies to be effective in providing sustained pain relief in knee osteoarthritis. This study aimed to assess the efficacy of PEMF therapy for treating thumb

CMC OA pain.

Objectives: To determine the effects of PEMF therapy on thumb CMC joint pain

Endpoints: Numeric Pain Rating Scale (NPRS) at 4 weeks

Study Population: 60 participants over age 18 with diagnosis of thumb CMC OA

Phase: N/A

Description of Single outpatient orthopedic hand clinic

Sites/Facilities Enrolling

Participants:

[figure not shown]
Description of Study

PEMF device for 8 hours nightly for 4 weeks

Intervention:

Study Duration: 36 months **Participant Duration:** 6 weeks

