4 STUDY DESIGN

4.1 OVERALL DESIGN

This study is a single-center, double-blind, randomized, controlled trial. Participants will be randomly assigned to either the experimental group or control group in a block size of 10 with an allocation ratio of 1:1.

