5.5 STRATEGIES FOR RECRUITMENT AND RETENTION

Members of the study team will review the clinic schedule through EPIC each week to identify eligible patients and recruitment will be through phone calls of patients with diagnosis of thumb CMC OA or at the time of their clinic visit. A member of the care team will introduce the study to the patient. If the patient is interested in learning more and/or participating, a member of the research team will provide study-related information and obtain informed consent via written or electronic consent. Recruitment flyers will be posted at the Stanford Orthopaedic Clinic with study information. Patients who may qualify will have the option to reach out to the study coordinator if they are interested in participating. A member of the research team will provide study-related information and obtain informed consent via written or electronic consent If a patient consents to participate, the patient will be randomized into either the study group or the control group. Recruitment will involve 60 participants total.

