6.2 PREPARATION/HANDLING/STORAGE/ACCOUNTABILITY

6.2.1 ACQUISITION AND ACCOUNTABILITY

The PEMF and sham devices will be provided to the investigator by the device manufacturer (BioElectronics Corporation, Frederick, MD), consecutively numbered by the device manufacturer based on a randomization schedule with a block size of 10 and allocation ratio of 1:1.

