7.2 PARTICIPANT DISCONTINUATION/WITHDRAWAL FROM THE STUDY

Participants are free to withdraw from participation in the study at any time upon request.

An investigator may discontinue or withdraw a participant from the study for the following reasons:

- Pregnancy
- Significant study intervention non-compliance
- If any clinical adverse event (AE), laboratory abnormality, or other medical condition or situation occurs such that continued participation in the study would not be in the best interest of the participant
- Disease progression which requires discontinuation of the study intervention
- If the participant meets an exclusion criterion (either newly developed or not previously recognized) that precludes further study participation

Subjects who sign the informed consent form, and are randomized and receive the study intervention, and subsequently withdraw, or are withdrawn or discontinued from the study, will not be replaced.

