9.4 STATISTICAL ANALYSES

9.4.1 GENERAL APPROACH

Baseline characteristics and all primary and secondary outcome measures will be analyzed using chisquare and Fisher's exact tests for categorical variables, Mann-Whitney U-tests for between-group comparisons of ordinal or continuous variables, and the Wilcoxon signed rank test for within-group comparisons of ordinal or continuous variables, using a 2-sided level of significance of 0.05. A minimally clinical importance difference (MCID) of 2 is established for changes in the NPRS.

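### Does recruiting 60 when Section 9.2 asks for 54, with no SD or effect scale stated, show an error in the sample size?

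*Combined protocol and SAP*

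**What the plan says.** Section 9.2 is a single sentence: "54 participants (27 in each group, allowing for 10% withdrawals) was calculated to detect an estimated effect size of 1 in NPRS", with power 0.80 and alpha 0.05. It gives no SD, no unit for the effect and no test.

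The recruitment figure appears twice. The synopsis (Section 1.1) describes "60 participants over age 18 with diagnosis of thumb CMC OA", and Section 5.5 says "Recruitment will involve 60 participants total".

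Other sections that bear on the point:

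- Section 7.2: participants who have been randomised and have received the device, and who "subsequently withdraw, or are withdrawn or discontinued from the study, will not be replaced".
- Sections 4.1 and 6.2.1: randomisation is "in a block size of 10 with an allocation ratio of 1:1", and the manufacturer numbers the devices from a "randomization schedule with a block size of 10 and allocation ratio of 1:1".
- Section 9.4.1: testing is done "using a 2-sided level of significance of 0.05". Section 9.4.2 names the Mann-Whitney U-test for NPRS at 4 weeks and leaves out participants with missing data.
- Section 9.4.1 also states: "A minimally clinical importance difference (MCID) of 2 is established for changes in the NPRS".

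**The concern.** Two things stand out on a first reading.

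First, a total that already contains a 10% allowance should be the number randomised, yet the trial recruits six more. Because 54/0.9 is exactly 60, it looks as if the allowance was either described in the wrong place or taken twice. If 54 really was the randomised requirement, the 0.80 does not describe the 60-participant trial.

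Second, the 0.80 cannot be rebuilt from Section 9.2. The term effect size often means a standardised difference. On that reading 54 is far more than 80% power requires. If it means one NPRS point, the answer depends wholly on an SD that is not given.

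At stake is whether a reader can tell what difference the trial can detect, particularly beside the MCID of 2, and whether the trial might be smaller than its stated power requires.

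**Working it through.** **Inputs from the documents.** Total 54, 27 per arm, withdrawals 10%, effect 1, power 0.80, alpha 0.05 (Section 9.2). Two-sided testing (Section 9.4.1). Mann-Whitney U-test (Section 9.4.2). Recruitment 60 (Sections 1.1 and 5.5). Blocks of 10, 1:1 (Sections 4.1 and 6.2.1).

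**Assumptions.** Every SD below is assumed, because the documents give none. The Mann-Whitney test is given efficiency 3/π = 0.955 relative to the t-test, which holds for normal data.

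**Step 1. Can 54 be reproduced as written, with 1 meaning one NPRS point?**
The normal approximation is n per arm = 2 × SD² × (1.96 + 0.84)² / difference². With SD 1.2 and difference 1 this is 2 × 1.44 × 7.85 = 22.6, so 23. The exact two-sample t-test gives 23.6, so 24.
With withdrawals: 24/0.9 = 26.7, so 27 per arm and 54 in total. The sentence in Section 9.2 holds together as it stands with an SD of about 1.2.

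**Step 2. What SD does the stated 0.80 imply?**

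| Meaning of 54 | Evaluable per arm | SD at 80% power for one point (Mann-Whitney to t-test) |
|---|---|---|
| Randomised, as written | 27 × 0.9 = 24.3 | 1.19 to 1.22 |
| Evaluable | 27 | 1.26 to 1.29 |

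Both ranges are narrow and neither has a source in the documents. They do not favour one meaning of 54 over the other.

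**Step 3. Where could 60 come from?**
- Withdrawals: 54/0.9 = 60.
- Whole blocks: 54/10 = 5.4 blocks, rounded up to 6 blocks = 60.

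Both routes give 60 exactly, so the number alone cannot show which was used.

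**Step 4. What does recruiting 60 deliver?**
60 × 0.9 = 54 evaluable, 27 per arm.
- If 54 was the evaluable requirement, the trial meets it and power is the stated 0.80.
- If 54 was the randomised requirement, the trial exceeds it. The difference that has 80% power at 24.3 per arm has power 0.84 at 27 per arm, by t-test or Mann-Whitney.

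**Step 5. The standardised reading (1 = one SD).**
The t-test needs 16.7, so 17 per arm; 17/0.9 = 18.9, so 19 per arm and 38 in total. Mann-Whitney needs 16.71/0.955 = 17.5, so 18 per arm; 18/0.9 = 20 per arm and 40 in total. Power at 27 per arm is 0.950 (t-test) or 0.941 (Mann-Whitney). Here 54 and 0.80 do not match, but the mismatch is an excess of participants.

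**Step 6. How far does the missing SD matter?**
Mann-Whitney, two-sided 0.05, 27 evaluable per arm:

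| Assumed SD | Power for 1 point | Power for 2 points |
|---|---|---|
| 1.25 | 0.80 | >0.99 |
| 1.5 | 0.65 | >0.99 |
| 2.0 | 0.42 | 0.94 |
| 2.5 | 0.29 | 0.80 |

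Power for one point depends strongly on the SD. Power for two points stays at about 0.80 or more up to an SD of 2.5.

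**The case for a change.** The strongest case for a change is that Section 9.2 is the only basis for the stated power and cannot be checked. The sentence is complete, so a redaction does not explain the gap. If 54 was randomised, 0.80 is not the power at 60. If the effect is standardised, 54 and 0.80 contradict each other however 54 is understood. If it is one point, the design targets half of the MCID of 2, and at an SD of 2.0 power for that difference would be only 0.42. One rewritten paragraph would settle all of this.

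Part of this stands. The SD, the scale of the effect and the reason for 60 are missing, and a better paragraph would give them. The rest does not carry the point further:

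- Section 9.2 attaches 0.80 to 54 participants, and no section claims a power for 60. Enrolling above a requirement makes neither statement false.
- The mismatch of 38 to 40 against 54 arises only on the standardised reading. Naming NPRS directly after the effect of 1 makes scale points the more natural meaning.
- The low powers in Step 6 follow from assumed SDs. They show that the SD matters, not that the trial falls short.
- The test and its sidedness are missing only from Section 9.2; Sections 9.4.1 and 9.4.2 supply them.
- The MCID is set for changes in NPRS, whereas the primary analysis compares 4-week scores between groups. Setting 1 beside 2 is therefore only a loose comparison.

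**Conclusion.** The concern identifies incomplete reporting, not an error in the design. Two readings of Section 9.2 fit the one-point effect: 54 randomised with an SD near 1.2, or 54 evaluable with an SD near 1.26 to 1.29 and the withdrawal phrase misplaced. On both, 60 recruited with 10% lost leaves 27 evaluable per arm, at power 0.84 or 0.80 respectively. On the standardised reading the trial is larger than it needs to be, with power of about 0.94 to 0.95. No reading that reproduces the stated inputs shows a shortfall.

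This rests on withdrawals of about 10% as planned, on the usual efficiency of the Mann-Whitney test, and on an SD that cannot be verified. If the true SD is well above 1.3, power for one point is below 0.80; the documents neither support nor exclude that.

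Whichever explanation is right, 60 participants are recruited in six whole blocks, the same two-sided Mann-Whitney test is applied, and the same result is obtained. Once data are in, the precision of the estimate is judged from the observed spread rather than from the planning SD. The missing details can be given when the calculation is reported, and the plan needs no change.

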9.3 POPULATIONS FOR ANALYSES

The analysis dataset will be an intention-to-treat (ITT) analysis dataset including all randomized participants.

9.4 STATISTICAL ANALYSES

9.4.1 GENERAL APPROACH

Baseline characteristics and all primary and secondary outcome measures will be analyzed using chisquare and Fisher's exact tests for categorical variables, Mann-Whitney U-tests for between-group comparisons of ordinal or continuous variables, and the Wilcoxon signed rank test for within-group comparisons of ordinal or continuous variables, using a 2-sided level of significance of 0.05. A minimally clinical importance difference (MCID) of 2 is established for changes in the NPRS.

